5.0 STUDY OBJECTIVES AND CLINICAL HYPOTHESES

5.1 STUDY OBJECTIVES

To evaluate the IOP-lowering effect and safety of Bim SR compared with SLT in patients with OAG or OHT who are not adequately managed with topical IOP-lowering medication for reasons other than medication efficacy (e.g., due to intolerance or nonadherence).

5.2 CLINICAL HYPOTHESES

Bim SR will have an IOP-lowering effect that is noninferior to that of SLT in patients with OAG or OHT who are not adequately managed with topical IOP-lowering medication for reasons other than medication efficacy (e.g., due to intolerance or nonadherence). Bim SR administered intracamerally will have an acceptable safety profile in patients with OAG or OHT who are not adequately managed with topical IOP-lowering medication for reasons other than medication efficacy (e.g., due to intolerance or nonadherence).

6.0 ANALYSIS POPULATIONS

The primary eye of each patient will be randomized to receive either Bim SR or SLT treatment. Based on treatment randomization, the contralateral eye will receive SLT if the primary eye receives Bim SR (or vice versa). Per study design, each eye of every patient will provide data for the two study treatments separately, and the experimental units for treatment effect are individual eyes.

6.1 INTENT-TO-TREAT POPULATION

Patients whose primary eyes were randomized to receive either Bim SR or SLT treatment will be referred to as randomized patients. The intent-to-treat (ITT) population is defined as all randomized patients and will be referred to as the “ITT population”. Analyses using the ITT population will be based on the randomized treatment assigned to each eye.

6.2 PER-PROTOCOL POPULATION

The per-protocol (PP) population is defined as all patients in the ITT population who have no protocol deviations affecting the data for the primary efficacy analysis for all primary analysis visits (Week 4, Week 12, and Week 24), and will be referred to as the “PP population”.

Since the primary eye and contralateral eye of a patient will contribute data separately for the two different treatments in the study, the data from one eye can be excluded from PP analysis due to a protocol deviation, but the patient can still be included in PP population because of valid data from the other eye.

Examples of protocol deviations that will result in removal of data from PP analysis include but are not limited to the following cases:

- Eyes with no study treatment will be excluded from PP analysis, and
- For eyes that received both study treatments or swapped treatments, data after the wrong treatment will be excluded from PP analysis.

A separate document will be prepared to describe the data exclusion criteria and algorithm for PP analysis. Additional considerations for PP exclusion from the IOP analysis may include situations where out of time window for Hour 0 IOP data; concomitant medication (or procedure) that potentially affects IOP data but is not identified as a non-study IOP lowering medication (or procedure) in the eCRF; or, implant removal, etc.

All patients with data excluded from the PP analysis will be identified and finalized prior to the primary database lock and will be displayed in a data listing with reason(s) for exclusion.

6.3 SAFETY POPULATION

The safety population is defined as all patients who had received at least one study treatment (regardless of whether it was the randomized treatment or not) and will be used for the safety analyses. Both eyes in the safety population are included in the ocular safety analyses. Ocular safety assessments will be based on the treatment received in each eye at the first administration. If a patient received both SLT and Bim SR in the same eye, safety assessment for this patient will be summarized under the Bim SR treatment group.

6.4 DATA COLLECTED BUT NOT ANALYZED

Clinical lab test data, vital signs, pregnancy test, national eye institute visual functioning questionnaire, and general (non-ophthalmic) physical examination are collected only at Screening and will not be analyzed. Other data collected but not analyzed, will be described in the clinical study report.

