6.2 Safety Measures

The following will be collected and recorded on the appropriate eCRF page(s):

Adverse Events: All adverse events, from the moment the patient signs the informed consent form, will be monitored and recorded in the patient's source documents. All events will be reported to Allergan on an adverse event eCRF, including seriousness, severity, action taken, and relationship to study drug. If adverse events occur, the first concern will be the safety of the study patient.

Weight and Height: Weight will be measured in pounds (lb) or kilograms (kg) using a scale. Height will be measured in inches (in) or centimeters (cm). Height and weight will be measured at Screening as part of the demographic data; historical patient information and/or patient reports should not be used for either measurement.

Vital signs: Systolic and diastolic blood pressure and pulse rate will be measured after patients have been at rest (seated) for at least 5 minutes. Body temperature will be measured orally (or with an infrared forehead thermometer) and recorded as $^{\circ}$ F or $^{\circ}$ C.

Blood and Urine Sample Collection: Blood and urine samples will be collected for blood chemistry, hematology panels, and urinalysis by a central laboratory or designated regional facility.

Pregnancy: Females of childbearing potential will have pregnancy tests performed. Pregnancy test kits will be provided by Covance Central Laboratory Services or a designated regional laboratory and will be administered according to the instructions provided with the tests.

Measures of Ocular Safety:

Best Corrected Visual Acuity: Visual acuity tests will be performed at all scheduled visits except on any of the Bimatoprost SR administration days or SLT Administration Day. Manifest refraction using Snellen equivalent with a logMar chart (see Procedure Manual) will be performed at Screening; Baseline; Weeks 12, 24, and 52; and Months 18 and 24/Exit. At all other visits, the visual acuity technician will use the last manifest refraction performed and determine the Snellen equivalent visual acuity using the logMar chart. If there is a 2-line or more reduction in visual acuity from the last best-corrected visual acuity performed, a repeat manifest refraction in both eyes and best-corrected visual acuity will be performed.

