6.3.1.3 Vital Signs

The below vital signs will be measured at all patient visits and should be recorded prior to any invasive procedures.

- Pulse rate (beats per minute [bpm]): the patient should be resting in a seated position for a minimum of 5 minutes prior to measurement. Pulse rate is then counted over 30 seconds (and multiplied by 2 to obtain bpm).
- Blood pressure (mm Hg): the patient should be resting in a seated position for a minimum of 5 minutes prior to measurement. Systolic/diastolic blood pressure will be measured with a sphygmomanometer (manual sphygmomanometer or automated blood pressure measuring device).
- Temperature (°C/°F): the patient should be seated and the body temperature taken orally (or with an infrared forehead thermometer).

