7.3.4 Safety Analyses

Safety analyses will be performed separately for patients in the Bimatoprost SR 15 µg and Bimatoprost SR 10 µg safety populations. The Medical Dictionary for Regulatory Activities (MedDRA) nomenclature will be used to code adverse events and medical history. The number and percent of patients reporting treatment emergent adverse events will be tabulated based on the primary SOC and preferred terms. Summary tables will be generated for all adverse events regardless of causality as well as treatment-related adverse events for the entire study and by treatment cycle. Other safety variables include vital signs (blood pressure, pulse rate, and temperature) and pregnancy test results. Ocular safety will be evaluated through assessment of visual acuity and visual field, evaluation of macroscopic bulbar conjunctival hyperemia and iris color, assessment of endothelial cell density and corneal thickness, IOP measurement, and biomicroscopic and ophthalmoscopic examinations (including gonioscopy with Bimatoprost SR implant assessment, optic disc examination, and dilated fundus examination).

Ocular adverse events and safety variables attributable to each eye will be summarized by Bimatoprost SR or SLT eye, and nonocular safety variables will be summarized by patient.

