11.0 SAFETY ANALYSES

All safety analyses will be performed using the safety population. Unless otherwise stated, the last non-missing safety assessment before the SLT treatment (Day 1) will be used as the baseline for all analyses of that safety parameter. As indicated in Section 6.4, safety data collected at Screening for eligibility assessment will not be analyzed.

All safety analyses described in the section 11.0 will be performed both Bim SR 10 µg and Bim SR 15 µg.

Ocular safety will be evaluated through; ocular AEs, best corrected visual acuity, visual field examination, specular microscopy, macroscopic iris color assessment, macroscopic conjunctival hyperemia assessment, gonioscopy/angle assessment, biomicroscopy (using a slit lamp), lens assessment, optic disc examination, dilated ophthalmoscopy, pachymetry, and anterior segment-optical coherence tomography.

Non-ocular safety analysis includes non-ocular adverse events (AEs), clinical laboratory results, vital signs (blood pressure, pulse rate and temperature), and pregnancy test results.

Safety analyses will be summarized by study periods. Analysis study periods are defined as follows:

- **During the study:** Date of SLT treatment through Month 24/Exit visit/last study visit available.
- **Analysis Cycle 1:** SLT Treatment date (Day 1) through the second Bim SR administration date – 1. If the second Bim SR administration was not given to a patient, all safety assessments through Month 24/Exit visit/last study visit available will be included in analysis cycle1.
- **Analysis Cycle 2:** Second Bim SR administration date through Month 24/Exit visit – 1.
- **Analysis Cycle 3:** Third Bim SR administration date through Month 24/Exit visit – 1, valid for only Bim SR 15 µg.

All summaries will be based on the first treatment received in each eye (Bim SR or SLT). If a patient who received both SLT and Bim SR in the same eye, safety assessments will be summarized in Bim SR. For non-ocular safety measures, overall summaries will be presented regardless of study treatment. For ocular safety assessments, summaries will be presented for the periods of during the study, Analysis Cycle 1 and Analysis Cycle 2 as shown in Figure 11-1 below.

Figure 11-1 Analysis Cycle Illustration

| Treatment Schedule | Cycles for Safety Data Analyses | |
|--|---------------------------------|------------------|
| | SLT eye | BIM SR eye |
| Day 1, SLT administration | Analysis Cycle 1 | Analysis Cycle 1 |

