11.2 VITAL SIGNS

Vital signs (systolic and diastolic blood pressures [mmHg], pulse rate [bpm], and temperature [Celsius]) will be collected at baseline, but will not be analyzed.

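### The SAP omits vital signs on the incorrect ground that they are collected only at Screening, leaving out a non-ocular safety summary that the protocol plans and that SAP 11.0 still lists

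*SAP*

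**What the plan says.** Three places in the SAP deal with vital signs.

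- SAP 6.4 groups them with clinical laboratory tests, the pregnancy test, the VFQ-25 and the general physical examination, and says that all of these "are collected only at Screening and will not be analyzed".
- SAP 11.2 says that they "will be collected at baseline, but will not be analyzed".
- SAP 11.0 says: "Non-ocular safety analysis includes non-ocular adverse events (AEs), clinical laboratory results, vital signs (blood pressure, pulse rate and temperature), and pregnancy test results".

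The protocol treats them as an on-study safety measure. Section 6.2 lists them among the safety measures. Section 6.3.1.3 says: "The below vital signs will be measured at all patient visits". Section 7.3.4 says: "Other safety variables include vital signs (blood pressure, pulse rate, and temperature) and pregnancy test results", and adds that "nonocular safety variables will be summarized by patient".

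**The concern.** The SAP leaves out an analysis that the protocol plans, and the reason it gives does not fit the data. Not analysing an eligibility measurement taken once at Screening is unremarkable. Not analysing a measurement repeated over 24 months of treatment and follow-up needs a reason of its own, and the SAP has none. For laboratory data it does give one: SAP 11.3 explains that abnormal results reach the analysis as adverse events. Nothing similar is said of vital signs, and neither entry in the SAP amendment list (19.1 and 19.2) mentions a change.

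Acceptable safety is one of the protocol's two clinical hypotheses. If 6.4 and 11.2 are followed, the study reports will contain no summary of blood pressure, pulse or temperature after treatment, although the protocol says that non-ocular safety variables will be summarised.

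**Working it through.** No power or error-rate figure is involved. The check compares the stated collection times with the schedules and counts the visits.

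**Step 1. Count the vital-sign assessments** (Protocol Tables 2 to 6).

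| Block | Visits with vital signs | Number |
|---|---|---|
| Table 2 | Screening, Baseline, Day 1 | 3 |
| Table 3 | Day 4, Cycle 1 Day 2, Weeks 4, 8, 12, 15 | 6 |
| Table 4 | Week 16, Cycle 2 Day 2, Weeks 20, 24, 28, 31 | 6 |
| Table 5 | Weeks 36, 40, 44, 47, 52 | 5 |
| Table 6 | Months 13, 14, 15, 16, 18, 20, 22, 24/Exit | 8 |

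Total: 3 + 6 + 6 + 5 + 8 = 28. This equals the protocol's own maximum of 28 visits, so every in-person visit has vital signs. The 5 phone calls have none. SAP 6.4 describes 1 of the 28.

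**Step 2. Separate pre-treatment from post-treatment.** Protocol 6.3.1.3 requires vital signs before any invasive procedure, and Protocol 8.4.3.1 lists them ahead of the SLT on Day 1. The Day 1 reading is therefore pre-treatment. Under the SAP 11.0 rule (last non-missing value before SLT) it would normally be the baseline. Post-treatment maximum: 28 − 3 = 25. The SAP's own Tables 4-4 to 4-7 mark the same 25 (6 + 6 + 5 + 8).

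**Step 3. Size.** At the 10 µg enrolment target the ceiling is 25 × 160 = 4,000 records. A patient who never receives Cycle 2 has two fewer visits (25 − 2 = 23). If Months 13, 15 and 22 are also skipped, as the protocol allows under conditions, the figure is 23 − 3 = 20. A patient who stays to Month 24 thus has 20 to 25 scheduled readings, and 160 such patients would give 3,200 to 4,000. The assumed 10% discontinuation lowers this further. The 15 µg patients are not counted here.

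**Step 4. Check each item in the SAP 6.4 list.**

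| Item | When collected | Is Screening only correct? | Listed as analysed in SAP 11.0 | Specific SAP section |
|---|---|---|---|---|
| Vital signs | All in-person visits | No | Yes | 11.2: not analysed |
| Pregnancy test | Baseline and Month 24/Exit | No | Yes | 11.3.1: neither analysed nor listed |
| VFQ-25 | Baseline | No | No | 13.0: Baseline, not summarised |
| Laboratory tests | Screening, unless retested | Yes | Yes | 11.3: not analysed, reason given |
| Physical examination | Screening | Yes | No | None |

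The stated timing is wrong for three of the five items. Section 11.0 conflicts with the specific sections on three: vital signs, pregnancy tests and laboratory results. Protocol 7.3.4 names two of those, vital signs and pregnancy tests; it does not name laboratory results.

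**The case against.** The best defence is that the SAP's intent can be worked out. Two specific sections say that vital signs are not analysed, Table 17-1 gives them no analysis window, and 11.0 itself refers back to 6.4. The list in 11.0 also names laboratory results and pregnancy tests, which later sections remove, so it looks like general text left uncorrected. A SAP may also narrow a descriptive analysis. This is fair as far as it goes: a programmer would probably produce no table. It does not rescue the omission, because the only reason offered is factually wrong and the protocol still promises the summary.

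Four stronger readings are tempting, and the documents do not support them.

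- **A reader might infer that a treatment comparison is lost.** Each patient receives both treatments, one per eye, so blood pressure, pulse and temperature cannot be attributed to either. SAP 11.0 presents non-ocular measures regardless of study treatment.
- **A reader might infer that safety data are discarded.** They are collected, and non-ocular adverse events are still tabulated by system organ class and preferred term. What is missing is the descriptive summary.
- **A reader might count Day 1 as post-treatment,** giving 26 readings per patient and 26 × 160 = 4,160 records. The reading precedes SLT, so the ceiling is 25 and 4,000.
- **A reader might take Protocol 7.3.4 to require by-visit tables of change from baseline.** It asks only that non-ocular variables be summarised by patient. Nor is safety a separate second objective: Protocol 2.1 has one combined objective, and safety is the second hypothesis in 2.2.

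**Conclusion.** The point holds as an error in the plan as written. SAP 6.4 and 11.2 misstate when vital signs are collected and disagree with each other. They omit a summary that Protocol 7.3.4 plans and that SAP 11.0 still lists. The omission of pregnancy tests has the same conflict with 7.3.4. For laboratory results the fault is only that 11.0 was not brought into line with 11.3, and for the VFQ-25 only that the timing in 6.4 is wrong.

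The size is modest: at most 25 unsummarised post-treatment readings per patient, or about 4,000 records for 160 patients. That ceiling assumes full enrolment, Cycle 2 in everyone, no skipped visits and no dropout. The record count measures how much is left unsummarised, not how much safety information is lost. The primary efficacy analysis and the ocular safety analyses are unaffected. The correction should be made because it is cheap and the present text contradicts both the protocol and itself.

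**What to change.** 1. In SAP 6.4, remove vital signs and correct the collection times: pregnancy test at Baseline and Month 24/Exit, VFQ-25 at Baseline. Laboratory tests and the physical examination can stay as Screening items.
2. Replace SAP 11.2 with the actual schedule and a patient-level descriptive summary of systolic and diastolic blood pressure, pulse and temperature, giving the value and the change from the last pre-SLT value, separately for the 10 µg and 15 µg patients. If it is presented by visit, add a vital-signs row to Table 17-1.
3. Make SAP 11.0 agree with the revised 11.2 and with 11.3 and 11.3.1.
4. If the sponsor still prefers to omit vital signs or pregnancy tests, take them out of 11.0 and record the omission as a departure from Protocol 7.3.4, with a reason that fits the actual collection schedule.

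The cost is a few lines of SAP text and one or two standard descriptive tables on data already being collected. No procedure, visit or sample size changes.

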7.0 PATIENT ENROLLMENT, DISPOSITION AND COMPLIANCE

The number of patients in analysis populations (ITT, Safety, and PP) will be summarized for the overall study. The numbers and percentages of patients randomized by country and site will be presented. The numbers and percentages of patients who complete the study and the numbers and percentages of patients who prematurely discontinue the study will be presented overall and by analysis cycle as defined in [Figure 11-1](#), with categories of premature discontinuation reasons included.

The study completers will be defined as the patients who received at least one study treatment and marked as completed in the eCRF disposition page. A patient who received study treatment in the relevant cycle will be considered to have completed the analysis cycle, if (a) the patient is a study completer or (b) the patient received the subsequent study treatment (Bim SR).

8.0 DEMOGRAPHICS AND OTHER BASELINE DATA

Demographics and other baseline characteristics will be summarized descriptively for the ITT population.

8.1 DEMOGRAPHICS AND BASELINE CHARACTERISTICS

Demographic parameters (including age, age group, race, race group, ethnicity, sex) and baseline characteristics (weight [kg], height [cm], and iris color) will be summarized descriptively. Patient's age at Baseline (years) will be presented in categories of less than 45 years; between 45 years and 65 years, inclusive; and greater than 65 years. In addition, race will be further grouped as White versus non-White and Hispanic versus non-Hispanic (Ethnicity). The iris color will be summarized by color for each of the following categories: monochromic, heterochromic peripupillary, and heterochromic diffuse. In addition, the reason for not being adequately managed with topical IOP-lowering medications (memory loss, physical inability to administer medication, tolerability, and other) will be summarized at patient level.

8.2 BASELINE DISEASE CHARACTERISTICS

Baseline disease characteristics for each eye will be descriptively summarized by treatment of the eye for the following variables for the ITT population: diagnosis of either Open-Angle Glaucoma (OAG); primary, pseudoexfoliation, pigmentary, or Ocular Hypertension (OHT), baseline Hour 0 IOP (≤ 25 mm Hg or > 25 mmHg), iridocorneal angle Shaffer grade, and central endothelial cell density.

8.3 MEDICAL AND SURGICAL HISTORY

Abnormalities in patients' medical and surgical histories will be coded using the Medical Dictionary for Regulatory Activities (MedDRA), 23.1 or newer. The number and percentage of patients with non-ophthalmic medical and surgical histories at the time of randomization will be summarized separately by system organ class (SOC) and preferred term (PT) for the ITT population. Ophthalmic medical and surgical histories associated with the Bim SR eye and/or SLT eye at randomization will also be summarized separately for the ITT population by SOC and PT.

8.4 PRIOR AND CONCOMITANT MEDICATIONS

Medications will be coded using the current version of the World Health Organization Drug Global Dictionary and the anatomical therapeutic chemical (ATC) classification system.

Prior medications are defined as medications taken before the date of the first administration of study treatment. Concomitant medications are defined as those medications taken on or after the date of the first administration of study treatment. If a medication is taken before the date of the first administration of study treatment and continues after initiation of study treatment, it will be considered as both a prior medication and concomitant medication.

8.4.1 General Medications

Prior and concomitant non-ocular medications will be summarized by drug class and preferred name in the ITT population.

8.4.2 Ocular Medications

Prior ocular medications, washout ocular medications, concomitant ocular medications, and non-study IOP lowering medications will be summarized by eye identified by randomized treatment, drug class, and preferred name separately for the ITT population. A non-study IOP-lowering medication will be defined by the information provided by the investigator on electronic case report form (eCRF).

9.0 STUDY DURATION

Patients' study duration will be summarized using descriptive statistics for each treatment group using safety population. Duration of time on study (days) for each patient will be calculated as days from the SLT administration date to the last visit date as shown below.

- Study duration = the last visit date available or study exit date – Day 1 SLT administration date + 1.

